STUDY DESIGN General This open-label extension study will evaluate the safety of long-term twice-monthly administration of somavaratan in adults with GHD. This is an open-label, multicenter study open to subjects completing a Versartis adult GHD study as well as approximately 40 new somavaratan naïve subjects (either rhGH treatment naïve or currently receiving daily rhGH therapy). All subjects will receive twice-monthly (every 15 days \pm 2 days) subcutaneous (SC) somavaratan. Doses will be titrated to each subject's individual IGF-I responses based on the IGF-I level 7 days post-dose until a maintenance dose is achieved. Maintenance dose is defined as an IGF-I value between 0 and 2.0 SDS for two consecutive 7 day post-dose time points (Day 8, peak level). Subjects receiving somavaratan once-monthly in this study (Protocol 15VR8) or in a previous somavaratan study (Protocol 15VR7), will have their dose decreased by half (minimum dose of 20 mg, 40 mg for women on estrogen, rounded down to the nearest even number) and will be titrated per the Dose Titration Plan (Table 2). New subjects enrolling in this study will be assigned to one of two cohorts and will receive a starting dose of 20 mg twice-monthly (40 mg for women on estrogen) (Table 1) and will be

titrated per the Dose Titration Plan (Table 2). Maintenance doses may be adjusted further based on PD data at the discretion of the Investigator or Medical Monitor.

Table 1 Study Drug Starting Dose Information:

Subject Cohort Assignment	Fixed Starting Study Dose	Frequency of Administration
Cohort 1: Adults with GHD irrespective of age and gender	20 mg	Twice-Monthly
Cohort 2: Women receiving oral estrogens	40 mg	Twice-Monthly

Table 2 Dose Titration Plan

Downward Dose Titration		
IGF-I at Day 8	Cohort 1	Cohort 2
0 to 2.0 SDS	No change in dosing	No change in dosing
2.01 to 3.0 SDS	4 mg dose decrement	4 mg dose decrement
Greater than 3.0 SDS	10 mg dose decrement	10 mg dose decrement
Upward Dose Titration ¹		
IGF-I at Day 8	Cohort 1	Cohort 2
-1.0 to 0 SDS	4 mg dose increment	10 mg dose increment
Less than -1.0 to -2.0 SDS	10 mg dose increment	20 mg dose increment
Less than -2.0 SDS	20 mg dose increment	40 mg dose increment

1: Maximum allowable dose is 250.0 mg

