The PK parameter is somavaratan concentration and the PD parameters are serum IGF-I and IGFBP-3. All subjects will have blood samples collected for PK/PD assessments at Day 1 (pre-dose) and Days 8, 16, and 23 during Month 1 and at Day 1 (pre-dose) and at Day 8 monthly until dose stabilization is achieved. Once maintenance dosing is achieved, PK/PD samples will be collected quarterly at Day 1 and Day 8 in the first year and then every 6 months thereafter.

Immunogenicity

Immunogenicity will be assessed by measuring anti-somavaratan antibodies (anti-drug antibodies, ADAs) at baseline and every three months during the first year of this study and then every 6 months thereafter. Testing will follow a tiered approach consisting of screening, confirmation, titration and additional characterization of confirmed positive ADA samples.

Study Population

The study population will consist of adults age 18-75 who have well-established growth hormone deficiency (GHD). Eligible subjects will have completed a Versartis adult GHD study or will be included as new subjects who are either rhGH treatment naïve or transitioned from daily rhGH therapy to twice-monthly somavaratan. New subjects transitioning from daily rhGH therapy must discontinue daily rhGH use for a minimum of 14 days prior to somavaratan dosing. Dosing will be stratified by 2 cohorts (Cohort 1: adults with GHD irrespective of age and gender; Cohort 2: women receiving oral estrogen).

CRITERIA FOR INCLUSION AND EXCLUSION

Inclusion Criteria:

1. Female or male subjects, between 18 and 75 years (inclusive) of age, with the diagnosis of AGHD
2. Eligible subjects may be naïve to somavaratan or have previously received somavaratan in the setting of a prior Versartis study
 - Subjects naïve to somavaratan must have a documented medical history of GHD during adulthood according to the Endocrine Society guidelines¹⁴ (confirmatory testing should be done to document persistence of childhood onset GHD into adulthood if necessary).
 - Subjects who have previously received somavaratan in the setting of a prior Versartis study can be included in this study if they have not met a stopping criterion in the corresponding study and somavaratan was well tolerated as judged by the Investigator and the Medical Monitor.
3. Naïve subjects must have an IGF-I SDS value ≤ 0 at Screening
4. All subjects must agree to the contraceptive requirements outlined in Appendix 2, if applicable.

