Immunogenicity will be assessed by screening for anti-drug antibodies (ADAs) at baseline and every 3 months during the first year and every 6 months thereafter. ADAs will be measured on blood samples collected at troughs (pre-dose). Testing will follow a tiered approach consisting of screening, confirmation, titration, and additional characterization of confirmed ADA positive samples.

STATISTICAL METHODS

Safety data will be listed by subject and summarized by cohort using frequencies or descriptive statistics. All subjects who receive at least one dose of somavaratan will be included in the safety analysis. Summaries of all adverse events (AEs), serious adverse events (SAEs), and incidence of Grade 3 or 4 adverse events will be classified according to severity and relationship to study drug.

No formal hypothesis testing is planned for this extension study.

For continuous variables, descriptive statistics will include the number of subjects, mean, standard deviation (SD), median, minimum, and maximum. For categorical variables, descriptive statistics will include the number and percentage of subjects in each category.

Summaries of subject disposition, demographics, disease characteristics, and exposure and response to dosing of study medication will be provided.

Somavaratan ADAs will be summarized descriptively.

AEs, PK, and PD will also be descriptively summarized by ADA subgroup (positive, negative) to assess potential effects of ADA positivity.

TABLE OF CONTENTS

APPROVAL/SIGNATURE PAGE: SPONSOR AND CONTRACT RESEARCH ORGANIZATION	2
SYNOPSIS: PROTOCOL 15VR8.....	3
LIST OF ABBREVIATIONS AND DEFINITIONS OF TERMS.....	15
1 INTRODUCTION	22
1.1.1 Adult Growth Hormone Deficiency.....	23
1.1.2 Pediatric Growth Hormone Deficiency	24
1.1.3 Summary of Clinical Experience	26
2 STUDY OBJECTIVES.....	28
2.1 Primary Objective.....	28
2.2 Secondary Objectives.....	28
3 INVESTIGATIONAL PLAN.....	29
3.1 Overall Study Design and Plan.....	29
3.2 Rationale for Study Design.....	31
3.3 Dose Selection	31
3.4 Study Duration and Dates.....	32
3.5 Safety Review and Stopping Rules.....	32
3.5.1 Stopping Rules.....	32
STUDY POPULATION SELECTION	33
3.6 Study Population.....	33
3.7 Inclusion Criteria:	33
3.8 Exclusion Criteria:	34
3.9 Subject Withdrawals and Replacements.....	35
4 STUDY TREATMENT(S).....	36
4.1 Description of Treatment(s).....	36
4.1.1 Somavaratan Treatment	36
4.2 Treatments Administered.....	36
4.3 Selection and Timing of Dose for Each Subject.....	37

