1.1.3 Summary of Clinical Experience

The safety, tolerability and PK/PD responses to somavaratan have been studied in 108 subjects with documented GHD (40 adults, 68 children). Somavaratan is intended for use as a long acting rhGH. When administered in children as weekly, twice-monthly or monthly doses, somavaratan was safe and well tolerated as indicated by the low number of drug-related AEs that were mild, transient and of the type expected with growth hormone replacement. No new safety signals have emerged for somavaratan. In adults as well as children, drug exposure parameters (C_{max} and AUC) were proportional to dose. The ability of single dose somavaratan to significantly

increase IGF-I exposures for up to one month was demonstrated in both GHD children and GHD adults. Normalization of IGF-I exposures did not result in meaningful overexposure to IGF-I. In all, only 6 adults and 5 children had IGF-I levels above the normal range (IGF-I SDS > 2.0). These responses were transient and no pediatric subject had an average 30 day IGF-I exposure above the normal range during 6 months of treatment. As anticipated from prior experience with daily rhGH, the somavaratan dose required to normalize IGF-I was demonstrated to be higher in children than in adults.

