For new subjects, treatment is initiated at the fixed starting dose (20 mg or 40 mg, as per assigned cohort), with subsequent doses determined based on individual IGF-I response. IGF-I levels (ng/mL) will be checked at pre-dose (trough) and at 7 (± 1) days after dosing (Day 8, peak) until dose stabilization is achieved. The 7 day post-dose (Day 8, peak) IGF-I SDS value will be used to determine dose adjustments with a target range of 0 to 2.0 SDS. If the peak IGF-I SDS is below the target range (e.g., < 0 SDS), the dose shall be titrated up according to the Dose Titration Plan (Table 2). If the peak IGF-I SDS is above the target range (e.g., > 2.0 SDS), the dose shall be titrated down according to the Dose Titration Plan (Table 2). Once a subject has achieved an IGF-I SDS within the target range for two consecutive months, s/he will be considered dose stabilized and will continue to receive that maintenance dose for the remainder of the study unless further adjustment becomes necessary. After dose stabilization is achieved, IGF-I levels will no longer be tested monthly; maintenance subjects will have pre-dose and 7 days post-dose IGF-I levels drawn every 3 months for the first year, and then every 6 months thereafter. If a subject on maintenance dose has an IGF-I value outside the target range, further dose adjustments will be considered on an individual basis by the Investigator or Medical Monitor with the objective to achieve and maintain IGF-I SDS at Day 8 within target range

(IGF-I SDS 0 - 2.0). Any change in somavaratan dose in a subject that has achieved maintenance dosing will be followed by an ad-hoc Day 8 IGF-I measurement to ensure IGF-I values are within target range (0 and 2.0 SDS).

Subjects will be monitored for safety throughout their participation in the study. Safety will be monitored by physical examination, inspection of injection sites, vital signs, , clinical laboratory determinations (including complete blood count, chemistry, lipid profile, urinalysis, measurements of adrenal function, thyroid function, and glucose metabolism), ECG's (new subjects only), and immunogenicity assessments. Immunogenicity assessments will include anti-drug antibodies (ADA). All ADA positive samples will be characterized in an *in vitro* cell assay that determines if the serum sample can inhibit human growth hormone (hGH)-stimulated cell proliferation.

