8.4 Objectives

The primary objective of this study is:

- To evaluate the safety of somavaratan during long-term treatment in adults with GHD

The secondary objectives of this study are:

- To evaluate the dose (starting and maintenance) and the dose titration plan of twice-monthly somavaratan during long-term treatment
- To evaluate the immunogenicity of somavaratan during long-term treatment in adults with GHD by detection and characterization of anti-somavaratan antibodies (anti-drug antibodies, ADAs)

- To evaluate pharmacodynamic responses (IGF-I, IGFBP-3) during long-term somavaratan treatment

Somavaratan ADAs will be summarized descriptively.

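### Titrating dose on IGF-I attenuates the planned IGF-I comparison by antibody subgroup, and dose, which would carry much of the lost signal, is not planned by antibody status

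*Combined protocol and SAP*

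**What the plan says.** The Synopsis (Statistical Methods) states the ADA comparison: "AEs, PK, and PD will also be descriptively summarized by ADA subgroup (positive, negative) to assess potential effects of ADA positivity". The Synopsis paragraph on pharmacokinetics and pharmacodynamics defines the terms: "The PK parameter is somavaratan concentration and the PD parameters are serum IGF-I and IGFBP-3". Dose is in neither list. Section 8.4 does not repeat the subgroup comparison and says only "Somavaratan ADAs will be summarized descriptively".

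Dosing follows IGF-I. The Synopsis (Study Design) says "Doses will be titrated to each subject's individual IGF-I responses based on the IGF-I level 7 days post-dose until a maintenance dose is achieved". Section 3.1 says that the Day 8 "IGF-I SDS value will be used to determine dose adjustments with a target range of 0 to 2.0 SDS", and "If the peak IGF-I SDS is below the target range (e.g., < 0 SDS), the dose shall be titrated up". Once a subject is in maintenance the wording softens: "If a subject on maintenance dose has an IGF-I value outside the target range, further dose adjustments will be considered on an individual basis". Section 3.1 also moves IGF-I sampling from monthly to quarterly at that point, and to six-monthly after the first year.

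The Synopsis promises summaries of exposure and of response to dosing, with no split by ADA status. Section 8.1 presents all summaries by cohort. Dose and immunogenicity are both secondary objectives (Section 2.2), but nothing in the documents links them.

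**The concern.** Day 8 IGF-I is the variable that the titration controls. If antibodies blunt the response, Day 8 IGF-I falls, the dose goes up under Table 2, and IGF-I moves back toward range. ADA-positive and ADA-negative subjects are then drawn toward the same IGF-I, and part of the antibody effect moves into the dose, which the comparison does not look at.

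Concentration is not controlled in this way, but it cannot be read without dose either. Section 1.1.3 reports that Cmax and AUC "were proportional to dose", so a raw concentration mixes dose with clearance.

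At stake is a secondary objective. Section 1.1.2 reports that several ADA-positive paediatric sera inhibited growth hormone in vitro, too few to analyse against clinical endpoints. Neutralisation is therefore a live question, and similar IGF-I in the two subgroups would be weak evidence that it is absent.

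**Working it through.** **No figure to reproduce.** The documents give no sample size, power or effect size for the ADA comparison. The check is a reading of the text, simple algebra and illustrative simulation.

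**1. Size of the offset, algebraically.** Assume Day 8 IGF-I SDS = a + b·ln(p·d/20), with d the dose in mg and p the relative potency (1, or 0.5 if neutralised). At a fixed dose, halving potency lowers IGF-I by b·ln 2, which is 0.69, 1.04 and 1.73 SDS for b = 1.0, 1.5 and 2.5. If titration raises the dose by a ratio r, the remaining gap is b·ln(2/r). With b = 1.5 and r = 1.62 this is 1.5 × ln(1.235) = 0.32 SDS, against 1.04 with no titration.

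**2. Simulation of the titration rule.** From the protocol: Cohort 1 steps of Table 2, 20 mg start, 250 mg maximum, maintenance after two consecutive in-range Day 8 values. Assumed: a ~ N(0, 1.5), within-subject SD 0.4, a 4 mg floor, potency halved from Month 1, 3 or 6, quarterly checks in maintenance, 24 months, 20,000 subjects per arm. Two maintenance behaviours bracket the discretion that Section 3.1 allows: Table 2 reapplied at each quarterly check, or no increase once in maintenance. Gap is ADA-negative minus ADA-positive mean IGF-I SDS. Share is gap divided by the fixed-dose effect.

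| b | Fixed-dose effect | Onset | Reapplied: gap (share) | Mean dose ratio | No increase: gap (share) | Mean dose ratio |
|---|---|---|---|---|---|---|
| 1.0 | 0.69 | M1 | 0.27 (39%) | 1.47 | 0.26 (38%) | 1.47 |
| 1.0 | 0.69 | M3 | 0.30 (43%) | 1.43 | 0.36 (52%) | 1.44 |
| 1.0 | 0.69 | M6 | 0.35 (51%) | 1.36 | 0.47 (68%) | 1.35 |
| 1.5 | 1.04 | M1 | 0.26 (25%) | 1.66 | 0.29 (28%) | 1.70 |
| 1.5 | 1.04 | M3 | 0.32 (31%) | 1.62 | 0.48 (46%) | 1.59 |
| 1.5 | 1.04 | M6 | 0.40 (38%) | 1.59 | 0.69 (66%) | 1.46 |
| 2.5 | 1.73 | M1 | 0.25 (14%) | 1.81 | 0.28 (16%) | 1.81 |
| 2.5 | 1.73 | M3 | 0.30 (17%) | 1.80 | 0.69 (40%) | 1.65 |
| 2.5 | 1.73 | M6 | 0.39 (23%) | 1.71 | 1.34 (77%) | 1.31 |

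With continued adjustment, 14% to 51% of the effect stays visible in IGF-I. With no increase in maintenance, the share is 16% to 38% for Month 1 onset, 40% to 52% for Month 3 and 66% to 77% for Month 6. In that last scenario the median dose is 24 mg in both groups, so dose alone would miss what IGF-I shows. The two have to be read together.

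**3. A different response shape, at Month 18.** Assumed: linear response of 0.04 to 0.10 SDS per mg, between-subject CV about 50%, baseline about -2 SDS (SD 1, capped at 0), within-subject SD 0.4. Maintenance checks follow the protocol (quarterly, then six-monthly), again under both behaviours. The gap is about 0.3 to 0.5 SDS when ADAs are present from early titration, and about 0.6 to 1.05 SDS when they appear at Month 7. The mean dose ratio across these runs is about 1.3 to 1.8.

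**4. Concentration.** Assume concentration is proportional to dose divided by clearance. The ADA-positive to ADA-negative ratio is then the dose ratio divided by the clearance ratio. Take a dose ratio of 1.6, inside the simulated range. Pure neutralisation (clearance ratio 1) gives a concentration ratio of 1.6. Clearance raised 1.6-fold and fully matched by dose gives 1.6/1.6 = 1, which looks like no effect. Dose-normalised, the two cases are 1 and 1/1.6 = 0.63, and can be told apart.

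**The case against.** The strongest reply is that the effect is attenuated, not hidden, and that other readouts exist. Most of this stands.

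- **Maintenance.** Table 2 drives dose month by month only until maintenance. After that, low values lead to case-by-case decisions; Section 3.1 makes adjustment mandatory only above 2.0 SDS. (Section 4.2 speaks of monthly Day 8 evaluation for all subjects, but Section 3.1 is explicit that monthly testing ends.) ADAs arising late can therefore leave a visible fall in IGF-I; in the Month 7 runs that follow the protocol schedule, the ADA-positive mean lies below 0 SDS.
- **Concentration.** It is not titrated to a target. Under pure neutralisation a higher dose would show as higher concentration at equal or lower IGF-I, which the planned tables could reveal. A reader might infer that PK fails in the same way as IGF-I; it does not. Its weakness is that dose and clearance cannot be separated.
- **In vitro assay.** Section 3.1 sends all ADA-positive samples to an assay of growth hormone inhibition. That is a direct readout of neutralising capacity, so it would be wrong to say the plan has none. It does not show whether the subject needed more drug, and no summary by its result is stated.
- **Other variables.** AEs, trough IGF-I and IGFBP-3 are not titration targets. Trough IGF-I and IGFBP-3 still respond to dose, so they are partly offset too.
- **Deferred detail.** Section 8.1 calls itself brief and defers to a statistical analysis plan. No separate plan is in the text reviewed, so the omission is established only for these documents.
- **Descriptive study.** No hypothesis test is planned, and no conclusion of no ADA effect is pre-written. This limits the severity. It does not make the IGF-I table easier to interpret.

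**Conclusion.** The point holds in a limited form. Followed as written, the plan compares ADA subgroups on an IGF-I value that dosing steers toward a common range, without the dose needed to interpret it. The IGF-I comparison is biased toward no effect. The bias is strongest when ADAs are present during titration, which includes any rollover subjects already positive on entry, and weaker when ADAs arise in maintenance.

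With potency halved, the simulations give a Month 18 gap of about 0.3 to 1.05 SDS and a mean dose ratio of about 1.3 to 1.8. These figures rest on assumed response slopes, variability and ADA onset, none of which the documents supply. They show direction and order of size only.

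A reader might go further and infer that neutralisation would be invisible in this study. The documents do not support that: the target is 2 SDS wide, upward changes in maintenance are discretionary, concentration is free to move, and inhibition is assayed directly. The change is worth making because it is specific and nearly free, not because the immunogenicity objective fails without it.

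**What to change.** In the Synopsis statistical methods and in Section 8.4, extend the ADA comparison. Classify by ADA status at the visit, and present results within cohort and separately for rollover and new subjects:

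- current dose and maintenance dose in mg, and the within-subject change in dose and in Day 8 IGF-I from the last ADA-negative to the first ADA-positive visit onward;
- dose-normalised somavaratan concentration;
- the same summaries by in vitro inhibition result, where numbers allow.

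The splits are needed. Oral estrogen use sets both starting dose and upward steps (Section 4.2), so pooling cohorts would confound dose with estrogen. Rollover subjects start from half their previous dose (Section 4.2), and their Baseline, the last value before the first dose in this study (Section 8.1), is on treatment. For the same reason, give dose-normalised IGF-I change only where a pre-somavaratan baseline exists. State that IGF-I by ADA subgroup is to be interpreted together with dose.

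The cost is a few descriptive tables. Doses are already recorded in the web response system (Section 4.9.1), and PK, PD and ADA samples are already scheduled. No new samples, visits or changes to dosing are involved.

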Immunogenicity was assessed at 4 time points in Phase 1b, at three time points in Phase 2a, and at 3 time points in the Extension Study in all pediatric subjects enrolled in these two studies by measuring anti-somavaratan antibodies (anti-drug antibodies, ADA) in serum samples. The serum from all ADA-positive subjects was further characterized using an *in vitro* cell assay that determines if the serum sample can inhibit human growth hormone (hGH) stimulated cell proliferation.

ADAs were first observed at Month 3 and remained consistent at Months 6, 12 and 18. Analyses have been performed on Month 18 data to determine if ADA positive and negative subjects differed with respect to clinical endpoints. ADA status had no statistically significant effect on the incidence or type of related adverse events, height velocity, drug concentrations, IGF-I responses or IGFBP-3 responses. The serum from several ADA-positive subjects tested positive for the ability to inhibit hGH in an *in vitro* cell proliferation assay. However, there were too few subjects that showed *in vitro* cell inhibition to conduct meaningful analysis of the significance of these results on clinical endpoints.

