2.2 Secondary Objectives

The secondary objectives of this study are:

- To evaluate the dose (starting and maintenance) and the dose titration plan of twice-monthly somavaratan during long-term treatment
- To evaluate the immunogenicity of somavaratan during long-term treatment in adults with GHD by detection and characterization of anti-somavaratan antibodies (anti-drug antibodies, ADAs)
- To evaluate pharmacodynamic (PD) responses (IGF-I, IGFBP-3) during long-term somavaratan treatment

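### The only planned look at ADA effects on outcomes compares ADA-positive with ADA-negative subjects; adding a split of the positives by in vitro hGH inhibition, which is already measured, would keep an effect confined to inhibitory antibodies from being averaged away.

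*Combined protocol and SAP*

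**What the plan says.** **Analysis.** The Synopsis, under Statistical Methods, plans a general ADA summary and then adds: "AEs, PK, and PD will also be descriptively summarized by ADA subgroup (positive, negative) to assess potential effects of ADA positivity". Section 8.4 repeats only the general statement, "Somavaratan ADAs will be summarized descriptively", and names no subgroup, titer or inhibition category. Section 8.5 does not list ADA among the safety variables. Section 8.1 has all summaries presented by cohort and leaves detail to a separate statistical analysis plan, as does Section 9.10.

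**Data collected.** The Synopsis section on immunogenicity says: "Testing will follow a tiered approach consisting of screening, confirmation, titration, and additional characterization of confirmed ADA positive samples". Section 3.1 goes further: "All ADA positive samples will be characterized in an" in vitro cell assay of whether the serum inhibits hGH-stimulated proliferation.

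**Objective.** Section 2.2 sets a secondary objective of evaluating immunogenicity "by detection and characterization of anti-somavaratan antibodies", and Section 8.4 restates it. The Synopsis version of this objective mentions detection only.

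**Previous experience.** Section 1.1.2 reports that in children ADA status had no statistically significant effect on related adverse events, height velocity, drug concentration, IGF-I or IGFBP-3. Several positive sera inhibited hGH in vitro, but "there were too few subjects that showed" in vitro "cell inhibition to conduct meaningful analysis of the significance of these results on clinical endpoints".

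**The concern.** The Introduction describes IGF-I expression as a consequence of hGH receptor signaling and calls IGF-I the primary PD marker. An antibody that blocks hGH action is therefore the kind most plausibly linked to a weaker PD response. Grouping subjects who have such antibodies with those whose antibodies show no inhibition averages the two together.

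The pediatric program shows how this can play out: the two-group comparison was reported, and the question about inhibitory sera stayed open. The adult plan names the same comparison and no display that uses the inhibition result against an outcome, although the assay is run on every positive sample. What is at stake is whether the study report can say anything about inhibitory antibodies from data it already holds.

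**Working it through.** The plan gives no figure to reproduce: there is no hypothesis test, sample-size calculation, expected ADA rate or expected inhibitory share.

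**1. Dilution.** Let f be the share of ADA-positive subjects whose serum inhibits hGH in vitro, d the mean effect in them relative to ADA-negative subjects, and b the mean effect in the other positives.

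- Positive minus negative = f × d + (1 − f) × b.
- If the effect is confined to inhibitory antibodies, b = 0 and the difference is f × d.
- The planned contrast then keeps a fraction f of the true difference. With f assumed at 5%, 10%, 20% or 50%, it keeps 5%, 10%, 20% or 50%. The same holds for a difference in the proportion of subjects with an AE.

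The documents supply neither f nor d, so no value in SDS units or percentage points follows.

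**2. Titration.** Sections 3.1 and 4.2 adjust each dose toward a Day 8 IGF-I of 0 to 2.0 SDS. If titration offsets a share t of the effect on Day 8 IGF-I, the planned PD contrast shows f × d × (1 − t). Even inhibitory versus negative shows only d × (1 − t). The offset part would appear as a higher dose, and dose is not among the variables to be summarized by ADA subgroup. A split of PD without dose could therefore still miss the effect.

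**3. How small the inhibitory group could be.** Maximum enrollment is 250 (Section 3.1). The ADA-positive rate (10% to 50%) and f (5% to 20%) are assumptions.

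- Smallest: 250 × 0.10 × 0.05 = 1.25, about 1 subject.
- Largest: 250 × 0.50 × 0.20 = 25 subjects.

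Take 30% positive (250 × 0.30 = 75 positive, 175 negative). In outcome-SD units, with equal SDs, the 95% half-width for inhibitory versus negative is 1.96 × √(1/n_inh + 1/175):

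| Assumed f | n_inh = 75 × f | Half-width (SD) |
|---|---|---|
| 5% | 3.75 | 1.02 |
| 10% | 7.5 | 0.73 |
| 20% | 15 | 0.53 |
| 50% | 37.5 | 0.35 |

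The split removes the dilution but may leave a group too small for means. Splitting further by cohort would make the cells smaller still. Subject-level display therefore has to be part of the change.

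**The case against.** **The detail may come later.** Section 8 is a summary, and a fuller analysis plan is deferred. It could add the split. That stands as a limit: the point concerns the documents supplied. But the two-group comparison is a stated choice, and nothing supplied points beyond it.

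**The plan does not ignore titer and inhibition.** A reader might infer that it does. The documents do not support that: the general ADA summary can reasonably include both results, and the Synopsis has safety data listed by subject. What is missing is narrower, namely any display linking inhibition status to AEs, PK, PD or dose.

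**No conclusion of no effect is planned.** A reader might infer that the pooled table is meant to show ADAs are harmless. The plan rules out formal testing and inferential safety analysis, and in Section 1.1.2 the sponsor reported the inhibitory sera separately and said they were too few to analyze. The pediatric finding was also one of no statistically significant effect, which is not a demonstration of none.

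**No size can be given.** It is tempting to attach an IGF-I difference in SDS. The documents give no inhibitory share and no effect, and titration would shrink any sustained difference, so such a figure would be invented. The identity also takes non-inhibitory positives to have no effect, which the documents do not establish.

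**Finer splits are not warranted.** A high/low titer grouping may look natural, but the documents offer no cut-point, and follow-up is open-ended, so a maximum titer depends on time in study. They also give no basis for a fixed minimum group size.

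**Conclusion.** The point holds as a cheap improvement. The only stated analysis of ADA against outcomes uses two groups, while the study collects an inhibition result on every positive sample and has characterization as a secondary objective. An effect confined to inhibitory antibodies would be diluted in proportion to the inhibitory share of positives, and for PD it would be masked further by titration to IGF-I. The proportionality assumes that non-inhibitory positives have no effect. The magnitude is unknown. The retained fractions and group sizes above are illustrations under assumed rates, not estimates for this trial. Nothing in the plan is numerically wrong, and no unsupported conclusion is announced.

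**What to change.** In the statistical analysis plan:

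- Keep the positive/negative summary.
- Add a split of ADA-positive subjects into those with and those without in vitro inhibition, shown beside the negatives, for AEs, PK, PD and somavaratan dose. Pool over cohorts where cells are small.
- Where the inhibitory group is too small for summary statistics, replace them with subject-level profiles of titer, dose, PK, IGF-I and AEs over time.
- State that results for the pooled positive group do not by themselves support absence of an effect of inhibitory antibodies.
- Say how sample-level results define a subject's group, since the documents do not.

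The cost is some wording and a few extra displays. No new samples or assays are needed. The added cells may be small and will be descriptive only.
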